Section 5.0 Study Design Five of the forty patients to be enrolled on the study will be enrolled to a control group.

Section 5.4.2 Immune Recovery versus Control Group Section added to detail study schedule for control patients.

CONFIDENTIAL

STUDY DRUG: NIVOLUMAB

SARAH CANNON DEVELOPMENT INNOVATIONS STUDY NUMBER:

FINAL PROTOCOL DATE: 07 FEB 2020

VERSION 7

BMT 24

BMT 24 PROTOCOL SYNOPSIS

Title of Study:	A Phase II Single Arm Study of Nivolumab as Maintenance Therapy after Autologous Stem Cell Transplantation in Patients with Hodgkin Lymphoma at Risk of Relapse or Progression	
Sarah Cannon Development Innovations Study Number:	BMT 24	
Sponsor:	Sarah Cannon Development Innovations, LLC – Nashville, TN	
Study Duration:	The total duration of the study is planned to be 4 years (2 years enrollment and 2 years maximum follow-up).	Phase of Study: II
Study Centers:	This study will be conducted at 6 study sites.	
Number of Patients:	Up to 40 patients are planned to be enrolled in this study: 35 will receive study treatment and 5 patients will receive standard-of-care procedures and treatment both pre- and post-transplant.	
Objectives:	
Primary Objective The primary objective of this study is to:
 
 • Evaluate safety and tolerability of nivolumab as maintenance early after autologous stem cell transplant (ASCT) in patients with Hodgkin Lymphoma (HL) 
Secondary Objectives The secondary objective of this study is to:
 
 • Evaluate PFS at 12 months post-transplant when nivolumab is administered as maintenance in patients with HL after ASCT 
Exploratory Objectives The exploratory objectives of this study are to:
 
 • Correlate efficacy of nivolumab when given as maintenance after ASCT with programmed cell death protein-1 (PD-1) expression and other immune effector and regulatory cells • Correlate positron emission tomography (PET)- computed tomography (CT) negativity with PFS 	
Study Design:	This is a Phase II single-arm open-label study of nivolumab as maintenance therapy after ASCT in patients with HL at risk of relapse or progression.	
Study Drugs, Doses, and Modes of Administration:	Patients will receive nivolumab (240 mg IV) starting Day 45-180 post-transplant (±10 days) every 2 weeks for up to a maximum of 6 months of treatment. Five patients will receive standard-of-care treatment pre- and post-transplant as a control group to compare immune recovery.	

CONFIDENTIAL

STUDY DRUG: NIVOLUMAB

SARAH CANNON DEVELOPMENT INNOVATIONS STUDY NUMBER:

FINAL PROTOCOL DATE: 07 FEB 2020

BMT 24

VERSION 7

BMT 24 PROTOCOL SYNOPSIS

Inclusion Criteria:	
 1. Patients 18 years of age and older with HL who have received auto-HSCT in the previous 45-180 days. 2. Complete response (CR), partial response (PR) or stable disease (SD) to salvage therapy prior to ASCT 3. High risk of residual HL post-ASCT, as determined by one of the following: 
 • Positive PET scan defined by the Deauville scale 3-4 (Appendix C) and within 2 months of start of high-dose chemotherapy prior to ASCT • Refractory to frontline therapy • Relapse <12 months after frontline therapy • Relapse ≥12 months after frontline therapy with extranodal disease 4. Eastern Cooperative Oncology Group (ECOG) Performance Status score of 0-1 (Appendix A). 5. Adequate hematologic function defined as all of the following: 
 - Absolute neutrophil count (ANC) ≥1000/μL - Hemoglobin (Hgb) ≥8 g/dL (transfusions to reach this point are not permitted) - Platelets ≥50,000/μL (transfusion is not permitted) 6. Adequate liver function defined as all of the following: 
 - Alanine aminotransferase (ALT) and aspartate aminotransferase (AST) ≤2.5 × the upper limit of normal (ULN) - Total bilirubin ≤1.5 × ULN (unless the patient has Grade 1 bilirubin elevation due to Gilbert disease or a similar syndrome involving slow conjugation of bilirubin) 7. Adequate renal function defined as serum creatinine ≤1.5 mg/dL (133 μmol/L). 8. Females of childbearing potential must have a negative serum or urine pregnancy test result within 72 hours prior to the first dose of nivolumab and must agree to follow instructions for method(s) of contraception for the duration of treatment with nivolumab and for 7 months following their last dose of study drug (Appendix C). Females of non-childbearing potential are those who are postmenopausal greater than 1 year or who have had a bilateral tubal ligation or hysterectomy. 9. Male patients with female partners of childbearing potential and women patients of childbearing potential are required to use two forms of acceptable contraception, including one barrier method, during their participation in the study and for 7 months following last dose of study drug. Male patients must also refrain from donating sperm during their participation in the study and for 7 months following last dose of study drug (Appendix C). 10. Willingness and ability to comply with study and follow-up procedures. 11. Ability to understand the nature of this study and give written informed consent.
----------------------------	---

CONFIDENTIAL

STUDY DRUG: NIVOLUMAB

SARAH CANNON DEVELOPMENT INNOVATIONS STUDY NUMBER:

FINAL PROTOCOL DATE: 07 FEB 2020

BMT 24

VERSION 7

BMT 24 PROTOCOL SYNOPSIS

Exclusion Criteria:	
 1. Patients that have received an allogenic transplant. 2. Prior ASCT or current therapy with other anti-neoplastic or investigational agents. 3. Best response of progressive disease prior to ASCT 4. Patients with any autoimmune disease or a history of autoimmune disease. Patients with vitiligo, type I diabetes mellitus, residual hypothyroidism due to autoimmune condition only requiring hormone replacement, psoriasis not requiring systemic treatment, or conditions not expected to recur in the absence of an external trigger are permitted to enroll. 5. Any condition requiring systemic treatment with corticosteroids (>10 mg daily prednisone equivalents) or other immunosuppressive medications within 14 days prior to first dose of study drug. Inhaled steroids and adrenal replacement steroid doses >10 mg daily prednisone equivalents are permitted in the absence of active autoimmune disease. 6. Use of a study drug ≤ 21 days or 5 half-lives (whichever is shorter) prior to the first dose of nivolumab. For study drugs for which 5 half-lives is ≤ 21 days, a minimum of 10 days between termination of the study drug and administration of nivolumab is required. 7. Wide-field radiotherapy (including therapeutic radioisotopes such as strontium 89) administered ≤ 28 days or limited field radiation for palliation ≤ 7 days prior to starting study drug or has not recovered from side effects of such therapy. 8. Major surgical procedures ≤ 28 days of beginning study drug, or minor surgical procedures ≤ 7 days. No waiting required following port-a-cath placement. 9. Previously untreated brain metastases. Patients who have received radiation or surgery for brain metastases are eligible if therapy was completed at least 2 weeks prior to study entry and there is no evidence of central nervous system disease progression, mild neurologic symptoms, and no requirement for chronic corticosteroid therapy. 10. Pregnant or lactating 11. Acute or chronic liver, renal, or pancreatic disease. 12. Uncontrolled diabetes mellitus (fasting blood glucose >250 mg/dL). 13. Any of the following cardiac diseases currently or within the last 6 months: 
 - Left ventricular ejection fraction (LVEF) <45% as determined by multiple gated acquisition (MUGA) scan or echocardiogram (ECHO) - Corrected QT (QTc) interval >480 ms on screening electrocardiogram (ECG) - Unstable angina pectoris - Congestive heart failure (New York Heart Association (NYHA) \geq Grade 2 [Appendix B]) - Acute myocardial infarction - Conduction abnormality not controlled with pacemaker or medication - Significant ventricular or supraventricular arrhythmias (patients with chronic rate-controlled atrial fibrillation in the absence of other cardiac abnormalities are eligible) - Valvular disease with significant compromise in cardiac function 14. Inadequately controlled hypertension (i.e., systolic blood pressure [SBP] >180 mmHg or diastolic blood pressure (DBP) >100 mmHg) (patients with values above these levels must have their blood pressure [BP] controlled with medication prior to starting treatment). 15. Serious active infection at the time of treatment or another serious underlying medical condition that would impair the ability of the patient to receive protocol treatment.
----------------------------	--

CONFIDENTIAL

STUDY DRUG: NIVOLUMAB

SARAH CANNON DEVELOPMENT INNOVATIONS STUDY NUMBER:

FINAL PROTOCOL DATE: 07 FEB 2020

BMT 24

VERSION 7

Exclusion Criteria:	
16. Known diagnosis of human immunodeficiency virus, hepatitis B, or hepatitis C. Testing at baseline is not required.
 
17. Presence of other active cancers, or history of treatment for invasive cancer ≤ 5 years. Patients with Stage I cancer who have received definitive local treatment and are considered unlikely to recur are eligible. All patients with previously treated in situ carcinoma (i.e., non-invasive) are eligible, as are patients with history of non-melanoma skin cancer.
 
18. Psychological, familial, sociological, or geographical conditions that do not permit compliance with the protocol.

Statistical Methodology:	
The null hypothesis to be tested is that the true 12-month PFS is 50% against a two-sided alternative hypothesis of a 70% PFS rate. The 50% 6-month PFS rate was obtained from Recommendations for Initial Evaluation, Staging, and Response Assessment of Hodgkin and Non-Hodgkin Lymphoma: The Lugano Classification (Cheson et al. 2014, see Appendix F). A two-sided, one-sample log-rank test calculated from a sample of 36 evaluable subjects achieves 80.3% power at a 0.050 significance level to detect an improvement of 20% in 12-month PFS.
 
The probability that a subject experiences an event during the study is 0.4579. The expected number of events during the study is 16. It is assumed that the survival time distributions of both groups are approximated reasonably well by the Weibull distribution with a shape parameter of 1.00. These proportions assume an enrollment period of 18 months and a follow-up period of 12 months after the last subject is added. In order to allow for a 10% dropout rate, a total of 40 patients will be enrolled. The sample size was calculated using PASS version 14.

CONFIDENTIAL

STUDY DRUG: NIVOLUMAB

SARAH CANNON DEVELOPMENT INNOVATIONS STUDY NUMBER:

FINAL PROTOCOL DATE: 07 FEB 2020

BMT 24

VERSION 7

BMT 24 CONTACT INFORMATION

Sarah Cannon Development Innovations Contact Information:	Sarah Cannon Development Innovations [name] [name] [name] [contact]
Study Chair:	[name] Sarah Cannon Research Institute [name] [name] [name] [contact]
Safety Dept. Fax #: Safety Dept. Email:	[name] [contact]

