1.6 PD-1 Expression in Hodgkin Lymphoma

Studies have found high expression of PD-L1 in HL (Roemer et al 2016). Programmed cell death protein 1 (PD-1) blockade with nivolumab in clinical trials enrolling heavily pre-treated HL patients have resulted in response rates in over 85% of patients (Ansell et al. 2015). The most common drug-related AEs were rash and decreased platelet count with 9% of patients discontinuing due to toxic effects (Ansell et al. 2015). Data demonstrating the tolerability and

CONFIDENTIAL

STUDY DRUG: NIVOLUMAB

SARAH CANNON DEVELOPMENT INNOVATIONS STUDY NUMBER:

FINAL PROTOCOL DATE: 07 FEB 2020

BMT 24

VERSION 7

efficacy of PD-1 inhibition in HL patients make nivolumab a promising therapy to evaluate in the post-transplant setting.

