2.4 Endpoints

2.4.1 Safety Endpoints

- Type, incidence, severity, seriousness, and relatedness of AEs
- Laboratory abnormalities

CONFIDENTIAL

STUDY DRUG: NIVOLUMAB

SARAH CANNON DEVELOPMENT INNOVATIONS STUDY NUMBER:

FINAL PROTOCOL DATE: 07 FEB 2020

BMT 24

VERSION 7

- AEs leading to discontinuation

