6. DOSE MODIFICATIONS

If toxicity occurs, the toxicity will be graded utilizing the NCI CTCAE v4.03 (https://evs.nci.nih.gov/ftp1/CTCAE/CTCAE_4.03/CTCAE_4.03_2010-06-14_QuickReference_8.5x11.pdf), and appropriate supportive care treatment will be administered to decrease the signs and symptoms thereof.

There will be no dose reduction of nivolumab; however, treatment delays are allowed. If the toxicity does not resolve to NCI CTCAE \leq Grade 1 after 28 days, then the patient should be withdrawn from the study and observed until resolution of the toxicity.

The dose modifications to be used in this study are presented in Table 1.

CONFIDENTIAL

STUDY DRUG: NIVOLUMAB

SARAH CANNON DEVELOPMENT INNOVATIONS STUDY NUMBER:

FINAL PROTOCOL DATE: 07 FEB 2020

BMT 24

VERSION 7

Table 1 **Dose Level Modifications**

Adverse Reaction	Severity*	Dose Modification
Colitis	Grade 2 diarrhea or colitis	Withhold dose ^a
	Grade 3 diarrhea or colitis	Withhold dose ^a
	Grade 4 diarrhea or colitis	Permanently discontinue
Pneumonitis	Grade 2	Withhold dose ^a
	Grade 3 or 4	Permanently discontinue
Hepatitis	AST or ALT >3 and up to 5 × the ULN or total bilirubin >1.5 and up to 3 × the ULN	Withhold dose ^a
	AST or ALT >5 × the ULN or total bilirubin > 3 × the ULN	Permanently discontinue
Hypophysitis	Grade 2 or 3	Withhold dose ^a
	Grade 4	Permanently discontinue
Adrenal Insufficiency	Grade 2	Withhold dose ^a
	Grade 3 or 4	Permanently discontinue
Type 1 Diabetes Mellitus	Grade 3 hyperglycemia	Withhold dose ^a
	Grade 4 hyperglycemia	Permanently discontinue
Nephritis and Renal Dysfunction	Serum creatinine >2.5 and up to 6 × the ULN	Withhold dose ^a
	Serum creatinine >6 × the ULN	Permanently discontinue
Rash	Grade 3	Withhold dose ^a
	Grade 4	Permanently discontinue
Encephalitis	New-onset moderate or severe neurologic signs or symptoms	Withhold dose ^a
	Immune-mediated encephalitis	Permanently discontinue
Other	Other Grade 3 adverse reaction First occurrence	Withhold dose ^a
	Recurrence of same Grade 3 adverse reactions	Permanently discontinue
	Life-threatening or Grade 4 adverse reaction	Permanently discontinue
	Requirement for 10 mg per day or greater prednisone or equivalent for more than 12 weeks	Permanently discontinue
	Persistent Grade 2 or 3 adverse reactions lasting 12 weeks or longer	Permanently discontinue

*Toxicity was graded per NCI CTCAE v. 4.03.

^a Resume treatment when adverse reaction returns to Grade 0 or 1.

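### Inclusion 5 admits blood counts that are probably Grade 2, yet treatment resumes only at Grade 0-1 with no reference to the entry value, so a patient who recovers from a Grade 3 fall to the entry count can be withdrawn

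*Combined protocol and SAP*

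**What the plan says.** **Entry.** Inclusion criterion 5 (synopsis and Section 3.1) requires "Absolute neutrophil count (ANC) ≥1000/μL", "Hemoglobin (Hgb) ≥8 g/dL (transfusions to reach this point are not permitted") and "Platelets ≥50,000/μL (transfusion is not permitted"). Patients enter 45 to 180 days after transplant.

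**Hold and resumption.** Section 6 grades toxicity by CTCAE v4.03 and allows delays but no dose reduction. Table 1 has no row for blood counts, so a falling count is held under the catch-all row for a first Grade 3 reaction. Footnote a gives the condition for restarting: "Resume treatment when adverse reaction returns to Grade 0 or 1".

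**Withdrawal.** If a toxicity is not at Grade 1 or lower after 28 days, Section 6 continues: "then the patient should be withdrawn from the study and observed until resolution of the toxicity". Table 1 separately makes a Grade 2 or 3 reaction that persists for 12 weeks a reason for permanent discontinuation.

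**Endpoint.** Section 2.4.1 lists "AEs leading to discontinuation" among the safety endpoints, and safety is the primary objective (Section 2.1).

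**The concern.** The rule for restarting is an absolute grade, while the entry criteria admit a range of counts that probably lies outside that grade. For a patient who starts in that range, full recovery to the pre-treatment state does not satisfy the rule. Nothing in Section 6 or Table 1 says that a return to the patient's own entry value is enough.

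The route is foreseeable. Section 1.6 reports for nivolumab in Hodgkin lymphoma: "The most common drug-related AEs were rash and decreased platelet count". The patients are also recently transplanted, so low counts at entry would not be surprising.

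What is at stake is the meaning of a primary-objective endpoint. It would mix discontinuations in which a drug toxicity failed to resolve with discontinuations in which the count had returned to where it began. Without a comparison with baseline, a reader of the results could not separate the two.

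**Working it through.** The plan gives no figure to reproduce on this point. The check sets the rules side by side, then does one piece of arithmetic.

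**Step 1. Entry limits against grades.** The CTCAE v4.03 cut-points are not printed in the documents. Assumed: Grade 1 ends, and Grade 2 begins, below Hgb 10 g/dL, ANC 1500/μL and platelets 75,000/μL; Grade 3 begins below 8 g/dL, 1000/μL and 50,000/μL.

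| Count | Entry limit | Assumed Grade 1 floor | Grade 2 range admitted | Rise above the entry limit needed to reach Grade 1 |
|---|---|---|---|---|
| Hgb (g/dL) | 8 | 10 | 8 to <10 | 10 − 8 = 2 |
| ANC (/μL) | 1000 | 1500 | 1000 to <1500 | 1500 − 1000 = 500 |
| Platelets (/μL) | 50,000 | 75,000 | 50,000 to <75,000 | 75,000 − 50,000 = 25,000 |

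On these cut-points the whole Grade 2 range is eligible. The misalignment does not depend on the exact values: it exists for any Grade 1 floor above the entry limit and disappears only if the floor is at or below it.

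**Step 2. What triggers a hold.** A Grade 2 count alone triggers none. The catch-all row needs a Grade 3 adverse reaction, and Section 11.1.3 reserves that term for events caused by the drug.

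**Step 3. Worked path.** Platelets are 60,000/μL at entry (Grade 2), fall below 50,000/μL through a drug effect (Grade 3, hold), and return to 60,000/μL (Grade 2). The entry state is restored, but footnote a is not met until 75,000/μL, which is 75,000 − 60,000 = 15,000/μL above entry. If the count stays at 60,000/μL past day 28, Section 6 says the patient should be withdrawn.

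**Step 4. Other texts on recovery.**
- Time limit: 28 days in the Section 6 text; 12 weeks (84 days) in Table 1 for a persistent Grade 2 or 3 reaction. Neither allows restarting at Grade 2.
- Recovery level: Section 3.3 follows Grade 3 or 4 laboratory values after discontinuation only until they reach Grade 1 or 2. The same Grade 2 value ends laboratory follow-up but bars resumption.
- Baseline: Section 11.3.6 treats a pre-existing condition as an adverse event only if it worsens. That governs recording; Section 6 has no counterpart.

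**Step 5. How the withdrawal would be counted.** Section 11.3.3 makes a laboratory value an adverse event if it leads to a change in, or the end of, study drug. Section 3.3 lists laboratory abnormalities attributed to the drug as a reason to discontinue. Section 10.4.3 summarises adverse events that led to discontinuation. Together these make it likely that the case is counted, but no text says how a withdrawal under the 28-day rule is coded.

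**Step 6. Size per patient.** The denominator is the 35 patients planned to receive study drug (Section 5). Proportions with exact (Clopper-Pearson) 95% intervals:
- 1/35 = 2.9% (0.1 to 14.9)
- 3/35 = 8.6% (1.8 to 23.1)
- 5/35 = 14.3% (4.8 to 30.3)

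These show the scale of the endpoint. They do not forecast how many patients will be affected.

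**The case against.** The best defence is that an entry threshold and a recovery threshold after drug toxicity serve different purposes and need not be equal. Footnote a speaks of the reaction returning to Grade 0 or 1, not of the raw value. With Section 11.3.6 in mind, a count back at its pre-treatment level could be read as a resolved reaction. The path also has several conditions: a Grade 2 count at entry, a Grade 3 fall attributed to the drug, and failure to reach Grade 1 within 28 days in patients whose marrow may still be recovering. Section 6 says such a patient should be withdrawn, which leaves some room.

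Much of this stands. The case may be uncommon, and a withdrawal that follows a drug-caused Grade 3 event is not simply spurious. What does not stand is that Section 11.3.6 settles the matter: it concerns recording, and sites would have to import it into Section 6 on their own initiative, perhaps not all in the same way.

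A reader might infer more than the documents support:
- *That an entry-level count itself leads to withdrawal.* It does not; a hold must come first.
- *That bilirubin shows the same problem.* Criterion 6 makes its exception "unless the patient has Grade 1 bilirubin elevation due to Gilbert disease", so a patient back at that entry value is at Grade 1 and may resume. The ordinary entry limits (ALT/AST up to 2.5 × ULN, bilirubin up to 1.5 × ULN) do not exceed the points above which Table 1 withholds (3 × and 1.5 × ULN). The hepatic algorithm in Appendix G continues therapy when the cause is non-inflammatory.
- *That these patients are lost to follow-up.* Section 6 has them observed until resolution, Sections 3.3 and 7.4 require 100 days of adverse-event follow-up, Section 7.5 requires the one-year PET-CT after early treatment end unless the patient progresses or starts new therapy, and Section 7.6 provides follow-up for up to 2 years.
- *That the number affected can be estimated.* The documents give neither the share entering at Grade 2 nor the chance of each later step.
- *That laboratory results will be summarised without regard to baseline.* Section 10.4.3 does not specify the format.

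**Conclusion.** The point holds for blood counts only. The entry limits and the Grade 0-1 resumption rule are not aligned, and no text provides for a patient whose entry count is already above Grade 1. Read literally, the rules can withdraw a patient whose count is back at its entry value after a drug-related Grade 3 fall. The 28-day and 12-week limits, and the recovery level in Section 3.3, add to the ambiguity.

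The size is 2.9 percentage points of the discontinuation endpoint per affected patient; how many will be affected is unknown. The conclusion rests on two things the documents do not state: the CTCAE cut-points (any Grade 1 floor above the entry limit suffices) and the coding of such a withdrawal as a discontinuation for an adverse event. The sponsor should correct this because it bears on the primary safety objective and costs little. Confidence is moderate.

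**What to change.** 1. Reconcile Inclusion criterion 5, Section 6, Table 1 (including the 28-day and 12-week limits) and Section 3.3, so that they agree on how the resumption and withdrawal rules apply to a patient whose entry count is already above Grade 1. The choice of threshold is a clinical matter for the sponsor.
2. State how a withdrawal under the 28-day rule is coded for the discontinuation endpoint.
3. In Section 10.4.3, tabulate laboratory abnormalities as shifts from baseline grade, using the CBC and CMP already collected before Cycle 1.
4. List separately any discontinuation in which the value had returned to its entry level.

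The cost is a wording amendment, one extra table and a short listing. No new data are needed.

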STUDY DRUG: NIVOLUMAB

SARAH CANNON DEVELOPMENT INNOVATIONS STUDY NUMBER:

FINAL PROTOCOL DATE: 07 FEB 2020

VERSION 7

BMT 24

1. INTRODUCTION

1.1 Background

Hodgkin Lymphoma (HL) is a cancer that arises from germinal center or post-germinal center B cells. The disease has unique cellular composition distinguishing it from other B cell lymphomas and consists of small numbers of malignant Reed-Sternberg cells within an extensive but ineffective inflammatory and immune-cell infiltrate. Hodgkin Lymphoma accounts for approximately 10% of all lymphomas, leading to about 8500 new cases and 1120 deaths annually in the United States (Siegel et al. 2016). Hodgkin Lymphoma has a bimodal age distribution curve with a peak in young adults at approximately 20 years of age and in older adults around age 65 (Ries et al. 1997). Most patients affected by this disease are young adults.

